14. APPENDIX F: LABORATORY PROCEDURES

Research specimens

Research samples collected in this protocol will be used for both protocol-defined testing as well as future, undefined research supporting the protocol. All research sample aliquots will be given unique bar code designations that cannot be linked back to the recipient.

Patient samples will be collected as specified below.

- Peripheral Blood sample on day -7, pre-transplant: Whole blood, Plasma
- Peripheral Blood samples on day 56 post-transplant: Whole blood (donor DNA)
- Donor chimerism results will be recorded at the time nearest to the DNA sample collection
- Peripheral Blood samples at day -7, 7, 14, 21, 28, 56, 100, 180 post-transplant, and if the patient develops GVHD, two additional blood samples at the onset of symptoms that need treatment initiation and 28 days after treatment begins: Plasma

Samples processed into frozen cryovial aliquots will be shipped to the central Laboratory at IU every 6 months on dry ice by Fedex or UPS overnight priority.

Table 6: Collection, processing, and shipping procedures for patient blood samples for protocol-defined biomarker testing and for future undefined research

Time	Collection	Type of processing and	Specimen	Purpose	Shipping specifications
Day -7 pre- transplant	12 mL peripheral blood (two 6 ml fill EDTA purple-top tube)	Centrifuge the EDTA containing whole blood tube at 1000-1300 g or 2100 rpm for 10 minutes within 60 minutes of collection. Remove the separated plasma. Aliquot to 1-4 cryovials and freeze at - 80° C in a scientific grade freezer.	Plasma	Future Biomarker studies	Batch ship every 6 months, frozen on dry ice in a shipping container, Fedex overnight priority to the Well's CCRC Laboratory at IU.
	3 mL peripheral blood (one 3 ml fill EDTA lavender-top tube) Source of patient DNA	Gently mix the tube by gently inverting the tube for 60 seconds and freeze at - 80° C in a scientific grade freezer.	Whole Blood. Until extracted for DNA	Future Biomarker studies	Batch ship every 6 months, frozen on dry ice in a shipping container, Fedex overnight priority to the Well's CCRC Laboratory at IU.
Day 7 post- transplant	12 mL peripheral blood (two 6 ml fill EDTA purple-top tube)	Centrifuge the EDTA containing whole blood tube at 1000-1300 g or 2100 rpm for 10 minutes within 60 minutes of collection. Remove the separated plasma. Aliquot to 1-4 cryovials and freeze at - 80° C in a scientific grade freezer.	Plasma	Seven protein biomarker panel/ Future Biomarker studies	Batch ship every 6 months, frozen on dry ice in a shipping container, Fedex overnight priority to the Well's CCRC Laboratory at IU.
Day 14 post- transplant	12 mL peripheral blood (two 6 ml fill EDTA	Ficoll (without diluting the blood). Centifuge at 2000 rpm at room temperature for 30 minutes, without brake. Remove the separated plasma. Aliquot	Plasma/ PBMCs	Seven protein biomarker panel/ Future	Batch ship every 6 months, frozen on dry ice in a shipping container, Fedex overnight priority to

	purple-top tube)	to 1-4 cryovials and freeze at - 80° C in a scientific grade freezer. Then collect the "buffy coat" (PBMCs), Wash three times with cold sterile PBS 1X to remove Ficoll (1400 rpm 4C. 10 min.). Count cells. Freeze cells in 1 ml aliquots using 90% FBS and 10% DMSO: 1-5M/vial, at least 2 cryotubes up to 4 cryotubes. Gradual freezing: PBMCs are stored 24 hours (not more) in - 80°C in the ethanol blue box (Cryo-safe cooler , to achieve a -1°C /min. rate of cooling) and then transfer in liquid nitrogen (liquid phase being better than gas phase). See details of the protocol below		Biomarker studies	the Well's CCRC Laboratory at IU.
Day 21 post- transplant	12 mL peripheral blood (two 6 ml fill EDTA purple-top tube)	Ficoll; see protocol below.	Plasma/ PBMCs	Seven protein biomarker panel/ Future Biomarker studies	Batch ship every 6 months, frozen on dry ice in a shipping container, Fedex overnight priority to the Well's CCRC Laboratory at IU.
Day 28 post- transplant	12 mL peripheral blood (two 6 ml fill EDTA purple-top tube)	Ficoll; see protocol below.	Plasma/ PBMCs	Seven protein biomarker panel/ Future Biomarker studies	Batch ship every 6 months, frozen on dry ice in a shipping container, Fedex overnight priority to the Well's CCRC Laboratory at IU.
Onset GVHD treated with systemic steroids	12 mL peripheral blood (two 6 ml fill EDTA purple-top tube)	Ficoll; see protocol below.	Plasma/ PBMCs	Seven protein biomarker panel/ Future Biomarker studies	Batch ship every 6 months, frozen on dry ice in a shipping container, Fedex overnight priority to the Well's CCRC Laboratory at IU.
28 days post- treatment for GVHD	12 mL peripheral blood (two 6 ml fill EDTA purple-top tube)	Ficoll; see protocol below.	Plasma/ PBMCs	Future biomarker studies	Batch ship every 6 months, frozen on dry ice in a shipping container, Fedex overnight priority to the Well's CCRC Laboratory at IU.
Day 56- 60 post- transplant	12 mL peripheral blood (two 6 ml fill EDTA purple-top tube)	Ficoll; see protocol below.	Plasma/ PBMCs	Future Biomarker studies	Batch ship every 6 months, frozen on dry ice in a shipping container, Fedex overnight priority to the Well's CCRC Laboratory at IU.
	3 mL peripheral blood (one 3 ml fill EDTA lavender-top tube) Source of patient DNA	Gently mix the tube by gently inverting the tube for 60 seconds and freeze at - 80° C in a scientific grade freezer.	Whole Blood. Until extracted for DNA	Future Biomarker studies	Batch ship every 6 months, frozen on dry ice in a shipping container, Fedex overnight priority to the Well's CCRC Laboratory at IU.

Day 100 post- transplant	12 mL peripheral blood (two 6 ml fill EDTA purple-top tube)	Ficoll; see protocol below.	Plasma/ PBMCs	Future Biomarker studies	Batch ship every 6 months, frozen on dry ice in a shipping container, Fedex overnight priority to the Well's CCRC Laboratory at IU.
Day 180 post- transplant	12 mL peripheral blood (two 6 ml fill EDTA purple-top tube)	Ficoll; see protocol below.	Plasma/ PBMCs	Future Biomarker studies	Batch ship every 6 months, frozen on dry ice in a provided shipping container, Fedex overnight priority to the Well's CCRC Laboratory at IU.
Day 360 post- transplant	12 mL peripheral blood (two 6 ml fill EDTA purple-top tube)	Ficoll; see protocol below.	Plasma/ PBMCs	Future Biomarker studies	Batch ship every 6 months, frozen on dry ice in a shipping container, Fedex overnight priority to the Well's CCRC Laboratory at IU.

Isolation of Human Peripheral Blood Mononuclear Cells (PBMCs) and Plasma by Ficoll separation and cryopreservation Protocol

Purpose

This Standard Operating Procedure (SOP) describes procedures for the isolation and cryopreservation of Plasma and Peripheral Blood Mononuclear Cells (PBMC) from whole blood.

Scope

2.1 This procedure is to be utilized for processing blood samples for the isolation, cryopreservation, and storage of Plasma and PBMC samples.

Materials and Reagents

No.	Name	Description	Concentration
1.0	Purple top vacutainers	BD # 367863	
2.0	Ficoll or lymphoprep (sterile)	Amersham #17544202 (GMP grade)	Use undiluted.
3.0	PBS 1X (- calcium, - magnesium) (sterile)	Hyclone SH30256.02	
4.0	Cryotubes	Orange top for cells, Corning	
5.0	Cryotubes	Clear top for plasma	

Procedure

- Do not dilute the blood
- For blood samples of up to 11 ml, add 5 ml of ficoll to a 15 ml tube. For blood samples over 11 ml, use 10 ml of ficoll in a 50 ml tube.
 - > Layer cells dropwise onto Ficoll.
 - > Let the drops hit the side of the tube and settle slowly to avoid disturbing the meniscus.
- Centifuge see table below

Multi-Center GVHD Biomarkers and Biobank Centrifuge Instructions	
Parameter	Setting
RPM	2000
Time	30 minutes
Temperature	Room Temperature (20-24°C)
Brake	Off
Acceleration	Off

•

- Carefully observe the cloudy "buffy coat" at the interface between the layers.
- Collect first the plasma and distribute to 1-4 clear top tubes (1.5 to 1.7 ml in each of the tubes). Plasma samples are aliquoted without additives into cryovials and stored at -80°C.
- Then collect the cloudy "buffy coat" (= PBMCs), avoiding the Ficoll layer, using a 10 mL pipet (for 15 mL conical tube) or 25 mL pipet (for 50 mL Conical tube). Place into a clean 15 ml tube.
- Wash once with 15 ml sterile PBS 1X to remove trace of Ficoll (1400 rpm 4C. 10 min.)
- Wash PBMCs again with PBS 1X @ 1200 rpm, 4C. 5 min.
- Resuspend pelleted cells in PBS and count.

- Only if necessary (most of the time you don't need to), lyse residual erythrocytes.
- The last wash should be @900 rpm 10 min, to get rid of the platelets and trash).
- Freeze cells in 1 ml aliquots using 90% FBS and 10% DMSO: up to 30M/vial (see table below), at least 2 orange top cryotubes up to 4 orange top cryotubes. Gradual freezing: PBMCs are stored 24 hours (not more) in -80°C in the ethanol blue box (Cryo-safe cooler, to achieve a -1°C /min. rate of cooling) and then transfer in liquid nitrogen (liquid phase being better than gas phase).

PBMC Aliquot Instructions	
Number of Cells	Number of cryotubes
1 -10 million	Distribute in 2
10 - 20 million	Distribute in 3
20 - 35 million	Distribute in 3
35 million and over	Distribute in 4

References

- University of Michigan BMT laboratory SOP
- Baylor Institute for Immunology laboratory SOP
- HIV/AIDS Network Coordination SOP

15. APPENDIX G- CELLULAR PROTEIN BIOMARKER PANEL FOR VIRUS AND LEUKEMIA SPECIFICT CELL IMMUNE RECONSTITUTION PROTEIN BIOMARKER PANEL

1. SPECIFIC AIMS

Cellular populations in the peripheral blood may also serve as biomarkers for GVHD (e.g. Tregs). Therefore, we anticipate improving the panel by adding biomarkers of virus and leukemia specific T cell immune reconstitution that will be generated in collaboration with [name]. This integrated proteomic/cellular approach will provide not only candidate biomarkers but also insights in the complex pathology of GVHD.

Accumulating evidence suggests that low levels of circulating Tregs following allo-HSCT in humans are associated with a higher incidence of GVHD in adults, and a causal link between these phenomena is suggested by murine models that show infusion of donor Tregs at the time of transplant or shortly thereafter prevents GVHD while maintaining the graft-versus-leukemia (GVL) effect. We hypothesize that increased donor-derived Tregs detected in the peripheral blood of pediatric patients is associated with a decreased risk of GVHD while sparing the cell mediated immune response to virus and tumor antigens after allo-HSCT. These hypotheses are formulated from extensive preclinical and clinical data and will be tested as follows:

Aim 1: To determine whether increased functional Tregs post allogeneic HSCT is associated with decreased GVHD without affecting cellular immune responses against leukemia and viruses.

We will evaluate patient peripheral blood samples. We will measure recovery of CD4⁺ CD25⁺ FoxP3⁺ T cells as well as other major T-cell subsets using flow cytometry and confirm whether these cells are of donor or recipient origin. We will evaluate the ability of the CD4⁺ CD25⁺ Tregs to suppress alloreactive responses and analyze the mechanism should such suppression occur. We will also measure T-cell immune reconstitution to leukemia antigens (WT1, PR1, PRAME) and viruses (EBV, CMV and Adenovirus) after allo-HSCT. We will measure the frequency of virus and leukemia reactive T cells and test their functionality in cytokine secretion assays.

2. BACKGROUND AND SIGNIFICANCE

2.1 Regulatory T cells. A subpopulation of T cells that are CD4⁺ CD25⁺ plays a crucial regulatory role in the immune system. These Tregs control autoimmune processes1 and modulate post-transplant alloreactive responses. Tregs constitutively express the transcription factor FoxP3, which is a key regulator of Treg development in humans and mice.2-4 Intracellular expression of FoxP3 is one of the most specific markers for Tregs,5 although other markers such as CD4, CD25^{hi} and CD127^{lo}, may also define the most potent subpopulations.6 In short-term *in vitro* assays, Tregs suppress proliferation of both CD4⁺

and CD8⁺ T cells after polyclonal or antigenic stimulation in a cell contact-dependent and cytokine-independent manner.7 Moreover, interleukin 2 (IL-2) is essential for the generation of Tregs and crucial in maintaining their suppressive function.8 Murine models show that high numbers of Tregs infused at the time of allo-HSCT can prevent GVHD while preserving the GVL effect.9;10⁻11 Indeed, if Tregs present in the transplant product are depleted prior to infusion into irradiated allogeneic recipient mice, GVHD is significantly accelerated.7 Additional studies have shown that Tregs infused post-transplant were able to control established GVHD.4

Human studies have demonstrated that poor Treg reconstitution post HSCT correlate with occurrence of acute or chronic GVHD.12·13 Phenotypic and PCR analyses of FoxP3⁺ regulatory T cells in 57 transplant recipients (27 with active, chronic GVHD and 30 without active, chronic GvHD) showed a decreased frequency of Tregs in patients with chronic GVHD compared to patients without (p<0.0001), and FoxP3 expression was reduced in chronic GVHD patients compared to those without or to controls (p=0.009 and 0.01, respectively).14 Furthermore, there is an association between high donor levels of FoxP3⁺ Tregs and a reduced risk of GVHD after HLA-matched allo-HSCT.15 The above data support efforts to determine in the pediatric setting whether rapid Treg immune reconstitution after allo-HSCT will prevent GVHD.

2.2 Recovery of cellular immunity after allo-HSCT. Normal immune reconstitution following HSCT extends over many months and even years, rendering the patient highly susceptible to bacterial, viral, and fungal infections as well as leukemia relapse. Viral infections are one of the leading causes of morbidity and mortality among allo-HSCT recipients. Reactivation of latent viruses such as Epstein-Barr Virus (EBV) and cytomegalovirus (CMV), and infection with community viruses such as adenovirus and RSV are frequent and significant causes of morbidity and mortality.16 Virus-specific T-cells are a critical protective element after allogeneic transplantation,17 and the most prolonged delays in virus-specific immune responses are associated with protocols specifying high levels of T-cell depletion and post-transplant immune suppression to prevent GVHD.

Similarly, several groups have looked at the immune reconstitution of tumor-specific T cells and their effect on relapse. Along with viral infection, we and others have shown that relapse is one of the main causes of failure after allogeneic stem cell transplant. T-cells specific for leukemia associated antigens such as the Wilms tumor antigen (WT1) have been shown to contribute to a graft-versus-leukemia (GVL) effect after allogeneic stem-cell transplantation (HSCT) for acute leukemia. Furthermore, loss of these leukemia specific CD8+ T-cell responses has been shown to be associated with relapse.18 *We hypothesize that a balanced regulatory and virus and leukemia specific T cell recovery prevents GVHD without delaying antiviral immune reconstitution.*

3. PRELIMINARY DATA

3.1. Preliminary data. To demonstrate our ability to measure the recovery of Tregs, NK cells and antigen-specific T cells, we isolated PBMC from transplant recipients immediately before and early (2-6 months) and late (>6 months) after transplantation (**Fig. 1A-C**). We plated the PBMC in a standard IFN- γ ELISPOT at a concentration of 2x10⁵ cells/well, and stimulated them with peptide mixtures (pepmixes) spanning the adenovirus hexon and

antigens, CMV IE1 and pp65 and the EBV antigens BZLF1, EBNA1, EBNA3A, EBNA3B and EBNA3C. To measure general T-cell function, we stimulated PBMC with Staphylococcus aureus (Staph) а positive as

penton

control, while unstimulated PBMC served as a negative control. Virus specific responses are shown in **Fig. 1B**. While we were able to detect robust specific T-cell reactivity to Staph early, we saw little evidence of virus-specific T-cell function in samples collected early (2 months) post-transplant. However, by 6 months after allo-HSCT, specific reactivity is detectable against viral antigens, indicating that patients who do not have GVHD can restore viral specific immunity within 3-6 months.19⁻²⁰ To detect tumor-specific T-cells, we stained the PBMC with HLA A2-restricted tetramers as shown in **Fig. 1C and D**. Detection of WT-1- and PRAME-specific T cells in the peripheral blood of patients with lymphoid and myeloid malignancies after allo-HSCT strongly correlated with a low relapse rate after transplant.18 These preliminary data support our proposal to detect antigen-specific T cells as well as NK cells, post-transplant in the peripheral blood of patients after allo-HSCT. Hence, these results demonstrate the feasibility of tracking the effects of BMSC infusions on post-transplant immune reconstitution in patients with GVHD.

4. RESEARCH PLAN

4.1. Immune reconstitution of T-cells and NK cells Blood will be obtained at the designated timepoints (Day +14, +21, +28, +56, +100, +180 and +360 post HSCT as well

as at time of complications such as acute and chronic GVHD onset, start of systemic steroids, or other complications). Peripheral Blood Mononuclear Cells (PBMC) will be obtained by Ficoll separation. Flow cytometric analyses will be used to quantify T cells (CD3+ CD4+ CD8) and T-cell subsets, including naïve and memory T cells, and NK cells. Once the T cells and NK cells have recovered to a predefined level (\geq 500 CD3⁺ cells/µL), samples will be frozen for batch analysis in the functional assays described below (4.2 to 4.5).

4.2. Are functional Tregs increased in pediatric patients without GVHD? To determine Treg phenotype, we will use the intracellular FoxP3 Treg kit (eBioscience) as well as CD4 and CD25 fluorescent antibodies (**Fig. 1A**). Treg induced suppression will be demonstrated by effects on thymidine uptake and CSFE assays in mixed lymphocyte reactions. Specifically, we will examine the response of T cells to a standard APC (Allogeneic PBMC or K562 cells expressing the high affinity IgG receptor CD64) loaded with OKT3. We will determine the mechanism for the suppression by measuring cytokine secretion (IL-10 and TGF- β). For thymidine uptake assays, PBMC will be separated into CD4⁺ CD25⁺ and CD4⁺ CD25⁻ fractions using fluorescent cell-sorting or magnetic bead separation. The CD4⁺ CD25⁻ fraction (responder cells) will be plated into a round-bottom 96-well plate coated with anti-CD3 (OKT3) or allogeneic PBMC. The CD4⁺ CD25⁺ Treg fraction will be added at a 1:1 ratio and incubated at 37⁰C. On day 3, each well will be pulsed with 1 μ Ci of ³H-thymidine. After 18 hours of additional incubation, plates are harvested and processed for counting.20

4.3. Do pediatric patients with GVHD have decreased pathogen-specific immune reconstitution compared to those without? Ten to 40 mL of blood (depending on the patient's size) will be taken at designated intervals post-HSCT to measure the frequencies of virus-specific T cells as well as NK cells. Absolute lymphocyte counts (ALC) will be measured to determine both absolute and relative frequencies of NK cells and virus-specific T-cells. Functional assays will determine the reconstitution of immunity to pathogens frequently detected in patients after allo-HSCT, including EBV, CMV, Aspergillus and adenoviruses.

(i) **Capturing viral reactivation.** Peripheral blood collected post-HSCT will be used for measurement of viral load (adenovirus, EBV and CMV), using PCR. These data will capture at each sample timepoint.

(ii) Immunity to common pathogens. To evaluate the immune response to EBV, CMV, Aspergillus and adenovirus, we will measure the precursor frequency of cytotoxic T lymphocytes (CTL) specific for these pathogens in ELISPOT assays.

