Samples will be collected at a time when clinical samples are being collected as well if possible. That is, this protocol will NOT require an additional procedure or for a patient's central venous line to be accessed at a time when these things are not being done as part of routine clinical care.

Blood will be collected as part of this study for use in evaluation of biomarkers of HSCT-related toxicities and outcomes and future unspecified research.

 Blood will be collected using the schedule detailed above: day -7 and the following post-transplant days: 7, 14, 21, 28, 56, 100, 180, and 360. Please note that the above blood draw schedule is a target only. Subjects will never be required to come for a clinic visit specifically to have samples collected for the purposes of this study. As such sample

samples collected for the purposes of this study. As such, sample time- points are targets and samples will be collected at the time closest to the target time when collection is feasible. In addition, during inpatient periods, sample collection will take place on the business day closest to

the day scheduled per protocol (to allow for flexibility around weekends and holidays).

- Blood will also be collected at onset of acute GVHD and at day 28 after initiation of steroid therapy.
- In addition, blood will be collected at the onset of other changes in status, which may be clinically significant (such as suspected sinusoidal obstruction syndrome, respiratory distress, relapse, etc.).
- Blood volume to be collected:

Please note cumulative collection volumes at various points in time of participation are summarized in the table below and are detailed for patients >40 kg in text immediately below for clarity.

- Patients > 40 kg: up to 15 mL per time point)
 - 9 scheduled collections in year one = 135 mL
 - 2 scheduled collections in patients who develop acute GVHD = 30 mL
 - Maximum additional blood draws at the time of developing other complications will be set at **four**.
 - 9 scheduled collections + 2 additional collections GVHD collections (if applicable) + maximum of four additional collections with other complications = 15 collections maximum = maximum blood draw of 225 mL.

	Patient Size on Enrollment			
	> 40 kg	25-40 kg	10-25 kg	<10 kg
Maximum volume of each scheduled blood draw	15 mL	10 mL	7.5 mL	5 mL
Maximum volume of blood of each blood draw if develops acute GVHD	15 mL	10 mL	7.5 mL	5 mL

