Maximum volume of blood with each complication	15 mL	10 mL	7.5 mL	5 mL
Maximum volume for scheduled blood draws (9 collections)	135 mL	90 mL	67.5 mL	45 mL
Maximum blood volume if develops acute GVHD (2 collections)	30 mL	20 mL	15 mL	10 mL
Maximum blood volume for other complications (4 collections)	60 mL	40mL	30 mL	20 mL
Maximum volume collected in year one (scheduled plus collections with complications)	225 mL	150 mL	112.5 mL	75mL

Table 4: Summary of maximum blood volume to be collected for this study

*Cumulative blood volume will be monitored for each subject and individual blood draws will be decreased as needed to maintain annual cumulative blood collection of <10% of total blood volume.

Also note, for pediatric patients, we expect patient weights to increase over time due to normal growth and as such, updated patient weights will be used to re-calculate permitted blood volume collections every six months.

GVHD scoring

Acute GVHD

A sample Acute GVHD data record for use in this trial is attached below.

Today's Clinical Acute GVHD Assessment						
Today's date Patient ID		Karnofsky/Lansky				
Codes		Differential diagnosis				
0 1 2 3 4		GVHD Drug Cond Infect TPN VOD Other				
		Rxn Reg				
Skin 🗆 🗆 🗆 🕬	oody rash:					
Liver 🗆 🗆 🗆 🗆 Curr	ent bili: [Lower				
GI 🗆 🗆 🗆 🗆 Vol:		□ □ □ □ Upper GI				
		Systemic				
agents: 🗌 CSA 🗌	Tacrolimus	🗌 Infliximab 🛛 🗍 Daclizimab				
Pentost	atin 🛛 Sirolimu	s				
Prednis	one 🗌 Methylp	rednisolone 🗌 Ontak 🗌 Other				
Current steroid dose: Prednisone	mg/	kg/day; Methylprednisolone mg/kg/day				
Has the steroid dose been increased to $\ge 2.5 \text{ mg/kg/day}$ of prednisone (or 2 mg/kg/day methylpred)? \square YES \square NO If yes, data dose increased						
Topical agents: Skin topical steroids: YES NO; Non-absorbed oral steroids (e.g. Budesonide, Entocort) Image: Chronic GVHD: Does the patient have evidence of chronic GVHD? YES NO						
Codes Skin	Liver (bilirubin)	Lower GI (stool output/day) Upper GI				
0 No rash	≤ 2 mg/dl	Adult: < 500 ml/dayNo protracted nausea andChild: < 10 ml/kg/day				
1 Maculopapular rash < 25% BSA	2.1-3 mg/dl	Adult: 500–1000 ml/dayPersistent severe nausea, vomiting with a positive upper GI biopsy				
2 Maculopapular rash 25 – 50% BSA	3.1-6 mg/dl	Adult: 1001-1500 ml/day Child: 20 – 30 ml/kg/day				
3 Generalized erythroderma (>50% BSA)	6.1-15 mg/dl	Adult: >1500 ml/day Child: > 30 ml/kg/day				

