4.6. Statistical analysis. The change in general immune reconstitution in patients with versus without GVHD will be summarized with descriptive statistics. After logarithmic transformation, if deemed appropriate, we will analyze the difference in changes by a two-sample t-test. In addition to descriptive statistics, Treg and antigen-specific T-cell immune reconstitution over time, as measured by phenotyping assays and functional assays will be plotted over time and represented as means ± SD.

4.7. Expected outcomes/potential problems. GVHD is known to be immune suppressive and we predict that there will be an increased Treg response in patients without GVHD with preservation of their cell mediated immune response. Given recent reports in the literature and our own preliminary data, we predict that if there is an increase in Tregs in patients without GVHD, that this will not dampen T-cell immune reconstitution against viral or

leukemia antigens. We also expect the immune reconstitution of NK cells to be unaffected in patients who do not have GVHD but that NK cells in patients with GVHD are either decreased and/or dysfunctional. Although unlikely, we cannot exclude the possibility that NK cells will not be detected in the periphery. This could reflect a complete loss of the NK cells or perhaps their limited expansion in vivo. It is also possible that T-cells and NK cells will home to sites of leukemia, prompting us to look for their presence in the bone marrow as well as blood. We do not anticipate any major obstacles with the proposed immune reconstitution studies, owing to our expertise at the CNMC in multiparameter flow cytometry and T-cell and NK cell functional immunoassays.24-26 However, it is entirely possible that smaller patients will have too few lymphocytes in their peripheral blood, especially in the early post-HSCT period, to accommodate the proposed testing scheme. If so, we will prioritize our tests, requesting additional samples if necessary. Phenotypic analyses, specifically for biomarker assays and CD4⁺ CD25⁺ FoxP3⁺ Tregs, will be performed first, followed by general phenotyping assays (T-cell subsets, NK cells and B cells), functional Treg assays and frequencies of CMV, then EBV and then adenovirus-specific CTL. In patients with evidence of viral infection, evaluation of the T-cell response specific to the infecting virus will be given priority.

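### Appendix G 4.3 sets 10 to 40 mL per interval, which conflicts with the section 4.2 per-draw blood caps: the minimum is too high below 25 kg and the maximum too high above 40 kg

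*Protocol*

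**What the plan says.** Section 4.2 of the Protocol contains a blood volume table (its Table 4), captioned "Summary of maximum blood volume to be collected for this study". The row "Maximum volume of each scheduled blood draw" gives 15, 10, 7.5 and 5 mL for patients above 40, 25-40, 10-25 and below 10 kg. The acute GVHD row and the row "Maximum volume of blood with each complication" repeat the same four figures. The accompanying text also sets 15 mL per time point as the limit above 40 kg. A footnote adds that "individual blood draws will be decreased as needed to maintain annual cumulative blood collection of <10% of total blood volume".

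Appendix G describes cellular assays. Its section 4.1 names days 14, 21, 28, 56, 100, 180 and 360, plus draws at complications. Its section 4.3, which asks about pathogen-specific immunity in pediatric patients, says "Ten to 40 mL of blood (depending on the patient's size) will be taken at designated intervals post-HSCT". Section 4.7 of the same appendix concedes that "it is entirely possible that smaller patients will have too few lymphocytes in their peripheral blood"; its response is to rank the tests and, if needed, to ask for more samples. It restates no volume limit.

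**The concern.** The two parts of one protocol give different volumes for what appear to be the same draws. All seven Appendix G days are scheduled draw days in section 4.2, and its complication draws fall under a capped row as well. The visible text gives Appendix G no separate allowance. Scaling by size does not settle the matter, because the smallest volume offered is 10 mL and two weight tiers have caps below that.

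The per-draw cap protects small children. A site that followed 4.3 literally in a child under 25 kg would exceed a limit that the protocol itself sets.

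**Working it through.** **Inputs.** Per-draw caps, subtotals and year-one totals come from the section 4.2 table; the 10 and 40 mL figures from Appendix G 4.3; the seven days from Appendix G 4.1.

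**Reproducing the table.** Each figure is the cap times the number of draws: 9 scheduled, 2 for GVHD, 4 for complications, 15 in all.

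| Weight | Cap (mL) | 9 draws | 2 draws | 4 draws | 15 draws |
|---|---|---|---|---|---|
| >40 kg | 15 | 135 | 30 | 60 | 225 |
| 25-40 kg | 10 | 90 | 20 | 40 | 150 |
| 10-25 kg | 7.5 | 67.5 | 15 | 30 | 112.5 |
| <10 kg | 5 | 45 | 10 | 20 | 75 |

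All entries match the protocol, so the table is internally consistent and the caps are as read.

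**Appendix G minimum against the cap.**
- <10 kg: 10/5 = 2.0, an excess of 5 mL.
- 10-25 kg: 10/7.5 = 1.33, an excess of 2.5 mL.
- 25-40 kg: 10/10 = 1.0, at the cap.
- >40 kg: 10/15 = 0.67, within the cap.

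**Appendix G maximum against the cap.** Volume scales with size, so 40 mL is compared only with the top tier: 40/15 = 2.67, an excess of 25 mL.

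**Scheduled total.** Seven draws at the minimum give 7 × 10 = 70 mL. The nine-draw scheduled maximum is 67.5 mL at 10-25 kg and 45 mL below 10 kg, so seven draws already exceed it by 2.5 and 25 mL.

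**Does the yearly footnote resolve it?** This needs a blood volume per kg, which the documents do not give. I assume 70-80 mL/kg, so 10% is 7-8 mL per kg. Draws on days -7 and 7 are taken at the cap and the seven Appendix G days at 10 mL.
- 15 kg, nine scheduled draws: 2 × 7.5 + 7 × 10 = 85 mL, against a limit of 105-120 mL. The footnote reduces nothing, yet seven draws exceed the 7.5 mL cap.
- 15 kg, all 15 draws, with the six event draws also at 10 mL: 2 × 7.5 + 13 × 10 = 145 mL, above 105-120 mL. The footnote reduces draws.
- Below 10 kg, nine scheduled draws: 2 × 5 + 7 × 10 = 80 mL. The limit is below 80 mL throughout this tier (56-64 mL at 8 kg), so the footnote reduces draws.
- At 8 kg, spreading what remains evenly over the seven days gives (56 − 10)/7 = 6.6 to (64 − 10)/7 = 7.7 mL, still above the 5 mL cap. With 13 such draws it would be 46/13 = 3.5 to 54/13 = 4.2 mL, below the cap.

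So the footnote sometimes brings draws under the cap and sometimes does not. It acts on the yearly sum, not on the single draw.

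**The case against.** The strongest reply is that sites would not take their volumes from Appendix G. It is written as a research proposal, and one line even refers to cell infusions that this non-interventional study does not give. Collection is directed by section 4.2, Appendix F and a processing manual sent to sites. A stated study-wide maximum would naturally prevail over an approximate range in an assay description, and 4.7 of the appendix already accepts short samples from small patients. This is fair and makes an actual overdraw less likely. It does not remove the contradiction: 4.3 says what will be taken, and nothing visible says which text governs.

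The footnote also gives real protection. On the assumptions above it binds throughout the tier below 10 kg, where the excess ratio is largest.

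Several stronger readings are tempting and not supported:
- A reader might set 40 mL against the smallest children's cap. Size scaling puts 40 mL at the largest patients, so the case for small children rests on the 10 mL minimum alone.
- A reader might infer that the yearly 10% limit would be broken. The footnote requires draws to be cut before that happens.
- A reader might take the SAP's 170 of 415 subjects aged 10 or under (41%) as the number exposed. That is an age count. Weights are not reported, and the SAP describes plasma measurements on days -7, 7, 14 and 21, with no Appendix G assay.
- A reader might see a second conflict in the untiered 12 mL of Appendix F, Table 6. With the 3 mL tube it makes 15 mL, the cap above 40 kg, and the laboratory procedure provides for samples of up to 11 mL. Those volumes are probably nominal and establish no conflict.

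**Conclusion.** The inconsistency stands, at minor severity. Below 25 kg, 4.3 and the section 4.2 cap cannot both be followed: the minimum is 1.33 times the cap at 10-25 kg and 2.0 times below 10 kg. Above 40 kg the upper end is 2.67 times the cap. At 25-40 kg only the very bottom of the range is permitted.

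This rests on reading 4.3 as a volume per interval, which is its natural sense, and on Appendix G sharing the scheduled and event draws. If its draws were separate, they would add to the volume at the same time points. The 70 mL comparison further assumes sampling on all seven days. Consent text and some other pages are not in the available documents, so an allowance there cannot be excluded.

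The documents do not show that any child was overdrawn or harmed. No endpoint, power figure or analysis is affected. The SAP reports accrual between 2013 and 2018, so the correction now serves mainly the protocol record and any further use of this text.

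**What to change.** In Appendix G 4.3, replace the 10 to 40 mL range with the section 4.2 weight-tier maxima: up to 15, 10, 7.5 or 5 mL per draw for above 40, 25-40, 10-25 and below 10 kg. State that Appendix G uses the scheduled and event draws already listed in section 4.2, and that additional samples requested under Appendix G 4.7 count toward the same per-draw and yearly limits.

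This is a wording change in one appendix. The price is fewer cells for some assays in small children, which the test ranking in 4.7 already handles.
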